5.5.2 Oxaliplatin

Oxaliplatin is a potent, third generation platinum analog, that, similar to other alkylating agents, binds to DNA, forming intra-strand cross links and DNA adducts. These DNA abnormalities inhibit DNA replication and transcription. Oxaliplatin can be administered as a single agent, but is typically given in combination with 5FU (see FOLFOX, below). It can be safely administered in patients with hepatic or renal dysfunction. The primary side effects include neurotoxicity (cold hypersensitivity and paresthesias) which can be dose limiting and also increase with repeated cycles of administration. Additionally, oxaliplatin can cause nausea, vomiting, diarrhea, and myelosuppression, all of which tend to be relatively mild. Rarely, patients may experience laryngospasm at the time of administration, which is often ameliorated by slowing the infusion and co-administration of benadryl.

5.5.3 FOLFOX

The FOLFOX regimen is a combination of 5FU, oxaliplatin, and leucovorin. FOLFOX was initially investigated and proven to be effective in patients with metastatic colorectal cancer, and still remains a standard option for such patients. Additionally, FOLFOX has demonstrated clinical activity in a number of cancer types, including pancreatic, gastric, esophageal, biliary, small bowel, breast, and lung cancers. There have been several different iterations of the FOLFOX regimen, but the one most commonly used is modified FOLFOX-6, consisting of:

- Oxaliplatin, 85mg/m² IV on Day 1
- Leucovorin, 400mg/m² IV on Day 1
- 5FU, 400mg/m² IV bolus on Day 1
- 5FU, 2400mg/m², continuous infusion over 46 hours (by portable pump), days 1-3

Toxicities of FOLFOX are essentially those of the single agent regimens. There is no additive or synergistic increase in toxicities, except perhaps the nausea and vomiting, which is generally easily controlled with an appropriate anti-emetic regimen, and fatigue, which tends to peak on days 3-5, and can be moderate, but not severe. Myelosuppression can become significant enough as to delay therapy, which may be an issue when combined with ABT-888. Thus, for this protocol, to reduce the risk of significant myelosuppression, we will not include the 5FU bolus altogether. A similar strategy is employed routinely in clinical practice for patients with a poor performance status or significant co-morbidities.

5.6 Justification for the use of FOLFOX in Pancreatic Cancer

As described above, one standard option as first line therapy for patients with metastatic pancreatic cancer is single agent gemcitabine. Gemcitabine was approved after demonstrating a significant increase in overall survival over 5FU(19). However, in the last twelve years, dozens of clinical trials have been performed, attempting to improve efficacy over single agent gemcitabine. Remarkably, no clinically meaningful improvements have been obtained with regards to overall survival when gemcitabine was combined with a number of cytotoxic nor biological therapies (reviewed in(2)), and the overall survival consistently remains in the 6-7 month range for patients receiving first line therapy. Furthermore, the response rates for gemcitabine have been dismally low, and very consistently about 8%(2). Thus, the putative "standard" backbone of gemcitabine justifiably should be questioned and reconsidered.

The combination of 5FU and oxaliplatin (typically a FOLFOX iteration) as a therapeutic option for patients with metastatic pancreatic cancer has been promising. Numerous phase II trials have demonstrated intriguing overall survival rates in the first, and even the second line setting for patients with metastatic pancreatic cancer. For example, Ducreux, *et al*, demonstrated a response rate of 10% with an overall survival rate of 9 months in previously untreated patients with metastatic pancreatic cancer treated with 5FU + oxaliplatin(5). In another first-line trial, Ghoshn, *et al*, demonstrated a response rate of 27%, with a median overall survival of 7.5 months(6). Second line trials have demonstrated response rates of 2.5 to 23% and overall survival rates (as second line therapy) of 4 to 6 months(7, 20, 21).

Recently, the most promising data came from the results of the CONKO-003 trial. Patients who had progressed on gemcitabine were randomized to 5FU + oxaliplatin vs. 5FU alone. Patients treated with a combination of 5FU and oxaliplatin had a median overall survival of ~11 months as measured from the start of gemcitabine therapy, which is the longest seen in a Phase III trial(3). Surprisingly, a Phase III comparison of FOLFOX and gemcitabine has never been attempted.

5.7 Clinical Experience with ABT-888

A Phase 0 dose-ranging pharmacokinetic and pharmacodynamic study of ABT-888 has been completed(13). In this trial, 13 subjects with various types of advanced cancer received a single dose of single-agent ABT-888 (10 mg, n = 3; 25 mg, n = 3; 50 mg, n = 7). The pharmacokinetic results from this study demonstrated that ABT-888 is orally bioavailable and primarily cleared through renal excretion, with a half-life of 4 to 5 hours. Additionally, this study provided proof of mechanism, as tumor PARP inhibition (> 90%) was demonstrated in 5 out of 6 human tumor biopsies that were obtained 3 to 6 hours after dosing with ABT-888. No serious adverse events were reported for this study.

The efficacy of ABT-888 in combination with DNA-damaging agents (including carboplatin, irinotecan, and temozolomide) is being explored in several Phase I and Phase II clinical trials. For example, a Phase I study of ABT-888 in combination with temozolomide is near completion. ABT-888 was given at escalating doses twice a day (BID), days 1-7 and Temozolomide daily at 200mg/m², days 1-5 of an every 28 day cycle. Correlative studies revealed significant PARP inhibition in peripheral blood mononuclear cells at doses as low as 20mg of ABT-888 BID. No dose limiting toxicities (DLTs) were reported for the first 3 dose cohorts of ABT-888 (10 mg BID, 20 mg BID and 40 mg BID). However, at 80 mg BID, 2 of 3 subjects enrolled experienced Grade 4 thrombocytopenia or neutropenia, and at 60 mg BID, 1 of 3 subjects enrolled experienced Grade 4 thrombocytopenia or neutropenia. Thus, 20 to 40 mg of ABT-888 BID have been the starting doses of ABT-888 combined with standard doses of chemotherapy for subsequent Phase II trials. However, in other trials a much higher dose of ABT-888 has been safely used. For example, our ongoing trial of ABT-888 plus FOLFIRI (5FU and irinotecan) has increased to 160mg of ABT-888 BID as of September, 2011, with further dose escalation anticipated. The optimal dose of ABT-888 with 5FU and oxaliplatin has not been identified. For this reason, a Phase I trial will first be performed to demonstrate safety with the combination of ABT-888 and 5FU and oxaliplatin, as well as to determine the Recommended Phase II dose of the combination.

ABT-888 is being used for 7 days, as was done in the Phase I trial of ABT-888 and temozolomide, and as is currently being replicated in multiple Phase II trials of ABT-888 plus other chemotherapies. The specific rationale is based on the intention that the PARP inhibitor (ABT-888) be present in the patient for significantly longer than the time that the DNA-damaging agent is impacting cancer cell DNA. This would in theory prevent cellular DNA repair, leading to overwhelming DNA damage and presumably cancer cell death.

6.0 INDICATIONS

Metastatic pancreatic cancer

7.0 STUDY OBJECTIVES

7.1 Primary Objectives:

7.1.1 Primary Objective of Phase I Portion: To determine the Recommended Phase II Dose (RP2D) of ABT-888 combined with 5FU and oxaliplatin in patients with metastatic pancreatic cancer

7.1.2 Primary Objective of the Phase II Portion: To determine the objective response rate of ABT-888 combined with 5FU and oxaliplatin in patients with metastatic pancreatic cancer

7.2 Secondary Objectives

7.2.1 Secondary Clinical Objectives To determine, in patients with metastatic pancreatic cancer treated with ABT-888 combined with 5FU and oxaliplatin:

- 1) Disease control rate (CR+PR+SD at 6 months)
- 2) Progression free survival
- 3) Overall survival
- 4) Time to disease progression
- 5) Duration of disease control
- 6) Tolerability and safety of the combination
- 7) Degree of Neuropathy, as measured by the FACT/GOG-NTX-4 (Version 4)

7.2.2 Secondary Scientific Objectives To associate the response rate of ABT-888 plus 5FU and oxaliplatin to:

- 1) Tumors that have decreased expression of or mutations in BRCA-1 or -2 or related pathway genes
- 2) PARP activity levels in serial tumor samples
- 3) Expression levels of DNA repair enzymes in tumor tissues
- 4) Pharmacokinetic and pharmacogenomic parameters associated with the metabolism of ABT-888
- 5) To isolate and propagate tumor cell lines obtained from patient samples and circulating tumor cells

8.0 TRIAL DESIGN

8.1 Treatment Plan

This is stratified single-treatment, open-label Phase I/II study to evaluate the clinical activity of the combination of the novel inhibitor of Poly(ADP-ribose) polymerase (PARP), ABT-888 with 5FU and oxaliplatin, *without the 5FU bolus* in patients with metastatic pancreatic cancer. Patients with metastatic, unresectable pancreatic cancer and a known BRCA-associate genetic mutation OR family history suggestive of a breast or ovarian cancer syndrome (as defined below) who still have an adequate performance status and normal hepatic and renal function will be eligible. As many as 24+48 patients will be enrolled. Patients will be stratified into two groups: Untreated or previously treated:

- Untreated patients should have received zero prior therapies for metastatic disease.
 - i. They may have received prior adjuvant chemotherapy and/or radiation therapy, but not within 6 months prior to treatment.
 - ii. They may have received prior *palliative* radiation therapy for unresectable disease, but without any systemic chemotherapy, even as a radiosensitizer
- Previously treated patients may have received any number of prior therapies, including prior adjuvant chemotherapy and/or radiation therapy within 6 months of treatment.

Cohort	ABT-888 (mg)
-1	20
1	40
2	60
3	80
4	100
5	150
6	200
7	250
8	300

The dose of ABT-888 will be determined by a Phase I dose escalation study. As detailed above, ABT-888 has been safely combined with traditional cytotoxic chemotherapy in previous clinical trials, though it has not been combined with 5FU and oxaliplatin. Therefore a traditional 3+3 dose escalation approach with doses of ABT-888 ranging from 40mg to 300mg twice-a-day will be employed to determine the RP2D of ABT-888 to be used with 5FU and oxaliplatin. Once the RP2D has been determined, all remaining patients will be enrolled in the Phase II portion of the study.

The starting dose of ABT-888 will be 40mg orally twice daily on days 1-7. Patients will be enrolled in a standard 3+3 dose escalating fashion to a maximal dose of ABT-888 of 300mg twice a day (Table 1). The *starting* doses of 5FU and oxaliplatin will not be adjusted, except that the 5FU bolus will be dropped. Patients will be enrolled in cohorts of three patients.

Table 1: Phase I Treatment Cohorts

However, given the concern over possible additive toxicity with the combination of ABT-888 and 5FU and oxaliplatin, the first patient for each dose level must have completed at least one full cycle, without any dose limiting toxicities before the last two patients in each cohort may be enrolled.

If there are no dose limiting toxicities (DLTs) in the first cohort, then three patients will be enrolled in the next cohort, as detailed in Table 1. Within any cohort, if one patient experiences a DLT, then the cohort will be expanded to 6 patients. If no additional patients experience a DLT, then three patients will be enrolled in the next cohort. If 2/6 or greater of the patients experiences a DLT, then the dose level below will be considered the MTD, and will be employed as the RP2D. The RP2D will be used for the Phase II portion of the study.

A dose de-escalation contingency has also been included (Table 1). If 2/6 or greater of the patients at Dose level 1 experiences a DLT, then patients will be enrolled at dose level -1. If 2/6 or greater of the patients at Dose level -1 experiences a DLT, then the trial will be terminated.

One cycle will be 14 days. Patients will receive 5FU and oxaliplatin without the 5FU bolus (oxaliplatin (85mg/m²) and leucovorin (400mg/m²) on day 1, followed by a continuous infusion of 5FU (2400mg/m²) over 46 hours on days 1-3). Patients will also receive ABT-888 twice-a-day on Days 1-7 of each 14-day cycle (Figure 1, above). The doses of 5FU, oxaliplatin, and leucovorin will be determined using the body surface area (BSA) calculated from the height obtained at the baseline evaluation and the weight obtained prior to each cycle. Subjects will self-administer the morning dose of ABT-888, and then the evening dose of ABT-888 will be taken approximately 12 hours after the morning dose.

As of April, 2013 (updated in Version 8.0, 04-15-2013), the recommended Phase II dose has been chosen to be 200mg of ABT-888 twice a day.

Study activities are presented in Table 3, and an early study activities checklist through cycle 2 is detailed in Table 4. Screening will occur within 14 days, prior to administration of the first dose of ABT-888 on Day 1 (baseline imaging scans must be done within 28 days of Day 1). All patients with biopsy-able tumor deposits will undergo the pre-treatment tumor biopsy prior to cycle 1, Day 1. During cycles 1 and 2, subject assessments (physical examinations including neurologic assessment, vital signs, performance status, medication review, chemistry, hematology and adverse event evaluations) will be conducted on Day 1 of each cycle. Beginning at cycle 3, patients will be seen on Day 1 of every other cycle (i.e. C3, D1; C5, D1; C7, D1, etc). Study procedures may be performed 2 days before or after the scheduled visit date, due to unforeseen or unavoidable circumstances. The neuropathy quality of Life assessment will occur during treatment for each odd-numbered treatment. Restaging studies will be performed every 4 cycles (or not more than every 12 weeks if there have been treatment delays). Patients who are adequately tolerating therapy, and whose restaging studies reveal no evidence of disease progression, by RECIST 1.1 criteria, will continue on study for an additional 4 cycles.

The primary endpoint of the Phase I portion is the determination of the recommended Phase II dose. The primary endpoint of the Phase II portion will be the objective response rate (ORR), as determined by RECIST 1.1 criteria. Secondary clinical endpoints are determination of the disease control rate (DCR, defined as ORR + rate of stable disease at 6 months), progression free survival (PFS), overall survival (OS), time to disease progression (TTP), duration of disease control (DDC), tolerability and safety of the combination, and degree of neuropathy, as measured by the FACT/GOG-NTX-4 (Version 4). Patients whose tumors have not progressed at the time of restaging, as determined by RECIST 1.1 criteria, and who continue to tolerate treatment will continue treatment for an additional eight weeks. When an investigator has determined that a subject should discontinue the study, a Final Visit will be conducted. Information pertaining to survival and post treatment therapy will be collected approximately every 12 weeks (Month 3, 6, 9, 12, 15 and 18) beginning after the final visit, for a period up to 24 months. Tumor biopsy procedures for the pilot subgroup are discussed in detail in section 12.

8.2 Selection of Study Population

This is a multi-institutional study for patients with metastatic pancreatic cancer. Only patients with metastatic pancreatic cancer not amenable for resection will be considered for entry. Subjects must have measurable disease, defined as at least 1 unidimensionally measurable lesion on a CT scan as defined by RECIST.

The target recruitment for this study is 24+48 patients. At the LCCC alone, approximately 150 new cases of pancreatic cancer are seen yearly, at least one-third of which have metastatic disease. Because patients with both untreated (for metastatic disease) and pretreated cancers are eligible, most patients seen in the medical oncology clinic with metastatic disease will be eligible for this trial. As of April 2013, the enrollment criteria were modified to include only patients with a known BRCA-associate genetic mutation OR family history suggestive of a breast or ovarian cancer syndrome (as defined below), which is likely to delay enrollment. However, concurrently, the trial is opening at several centers, which may compensate for the

slower accrual. Therefore, recruitment is anticipated to take 24 – 30 months, and with each patient followed for a minimum of 8 weeks, the anticipated time to complete follow-up of all patients will be 30 – 36 months.

Subjects will undergo screening procedures within 14 days prior to administration of the first dose of ABT-888 on Day 1, unless otherwise specified (though baseline imaging scans must be done within 28 days of Day 1). Adult male and female subjects who meet all the inclusion criteria and who do not meet any of the exclusion criteria will be eligible for enrollment into the study.

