13.4.2.3 Overall Survival

Overall survival will be defined as the time in days from study entry until death. Patients who are alive on the date of closing follow-up will be censored on that date. All events of death will be included, regardless of whether the event occurred while the subject was still taking study drug, or after the subject discontinued study drug. If a subject has not died, then the data will be censored according to the following rule: if the subject was lost to follow-up, then data will be censored at the last study visit, or the last contact date, or the date the subject was last known to be alive, whichever is later; if the subject was not lost to follow-up, then data will be censored at the last study visit or the last contact date, whichever is later. The date of the last study visit will be determined by selecting the last available date of the following study procedures for a subject: tumor assessment, physical examination including neurologic assessment, vital signs assessment, blood chemistry and hematology collection, and performance status.

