13.5.4 Timing of Efficacy Analyses and Safety Evaluations

As described above, this trial will follow a Simon's two-stage optimal design(1). Thus, by definition an interim efficacy analysis will be performed after the first 9 patients. A Data Safety and Monitoring Committee will also review the safety data quarterly and ensure that the early stopping rules are carried out as planned.

The date after which the 9th patient has received at least two cycles of therapy will be defined as the primary data "cutoff" date for the efficacy analyses (as detailed in Section 8). All data available at the time of database lock will be included in the efficacy and safety analyses. When data collection is complete and reviewed for completeness and all data management quality assurance (QA) and quality control (QC) procedures are

performed, the clinical database data will be extracted for documentation and statistical analyses. Once the last enrolled subject discontinues/completes the study, the study will be considered complete and all remaining data will be collected and entered into the clinical database. Overall survival will be collected on all subjects for up to 24 months after they discontinue from the study. After all survival data have been collected and entered into the clinical database, the clinical database data will be extracted once again for documentation and a "Final Analysis" will be performed on this dataset.

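### Overall survival has two censoring dates for patients who are alive and in contact; the closing-date rule can overstate 12-month survival slightly, and the stated follow-up timeline and contact list do not fit the 24-month survival window

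*Combined protocol and SAP*

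**What the plan says.** Section 13.4.2.3 defines overall survival from study entry to death. Its second sentence reads "Patients who are alive on the date of closing follow-up will be censored on that date". Further down, the same section introduces a rule for subjects who have not died. For those still in contact it says "if the subject was not lost to follow-up, then data will be censored at the last study visit or the last contact date, whichever is", and ends by choosing the more recent of the two dates. Subjects lost to follow-up have their own rule, the latest of last visit, last contact or date last known alive. The documents do not define the closing date.

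On how long survival is followed:

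- Section 8.2 forecasts accrual: "recruitment is anticipated to take 24 – 30 months". It sets the shortest follow-up in the words "with each patient followed for a minimum of 8 weeks" and then concludes that "the anticipated time to complete follow-up of all patients will be 30 – 36 months".
- Section 8.1 has survival information gathered "approximately every 12 weeks (Month 3, 6, 9, 12, 15 and 18) beginning after the final visit, for a period up to 24 months".
- Section 13.5.4: "Overall survival will be collected on all subjects for up to 24 months after they discontinue from the study". The Final Analysis comes "After all survival data have been collected and entered into the clinical database".
- Table 3 has a three-monthly column for progression and survival, with no stated end.

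Section 13.5.1.2.3 plans a Kaplan-Meier estimate of 12-month survival and of the median, each with a 95% confidence interval.

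**The concern.** Both censoring sentences apply to a patient who is alive and in contact. They give the same date only if that patient is contacted on the closing day. With contacts 12 weeks apart, most patients will not be, so two analysts following the section could produce different survival curves from the same database. The rules are not equally safe. Last-contact censoring credits only time during which the patient was known to be alive. Closing-date censoring also credits the time since the last contact, and a death in that gap that has not yet been reported is counted as survival. The error can only go upward.

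The size of the error depends on when follow-up closes, and on this the sections do not fit together. The date in 8.2 leaves no room for the window in 8.1 and 13.5.4, and the contacts listed in 8.1 end six months before that window does.

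**Working it through.** **The figure in 8.2.** Recruitment of 24 to 30 months plus the 8-week minimum (8 × 7 / 30.4375 = 1.84 months) gives 25.8 to 31.8 months, not 30 to 36. The stated figure is reproduced by 24 + 6 = 30 and 30 + 6 = 36, so it implies a 6-month tail after the last entry, which the section does not state.

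**The survival window.** For a last-enrolled patient who survives the whole window, 24 + 24 = 48 and 30 + 24 = 54 months, plus time on treatment. With 8 weeks on treatment that is 49.8 to 55.8 months. The date in 8.2 is 18 months or more short (48 − 30 = 54 − 36 = 18). Stopping at the last listed contact, Month 18, would still need 24 + 18 = 42 to 30 + 18 = 48 months plus time on treatment.

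**When the censoring choice can affect 12-month survival.** One contact interval is 12 × 7 / 30.4375 = 2.76 months. The rules differ before month 12 only for patients whose last contact falls before month 12.

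- Closing 24 months after the last entry: every survivor's last contact is at 24 − 2.76 = 21.2 months or later. The unverified gap lies wholly after month 12, so the effect is nil.
- Closing 6 months after the last entry: under uniform accrual, 6/24 = 25% (24-month recruitment) to 6/30 = 20% (30-month recruitment) of patients have under 12 months of potential follow-up. Their gap can fall before month 12.

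**Size.** Simulation with 24 patients (one stratum), uniform accrual, exponential survival, contacts every 12 weeks from entry, deaths learned only at a contact, no loss to follow-up, and 8,000 runs per setting. Medians of 4 to 9 months span the figures in section 5.6; 12 months is an added assumption. Mean Kaplan-Meier 12-month survival with a 6-month tail:

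| Median (months) | True | Closing date, 24-month accrual | Closing date, 30-month accrual | Last contact (24- / 30-month accrual) |
|---|---|---|---|---|
| 4 | 12.5% | 13.6% | 13.5% | 12.4% / 12.6% |
| 6 | 25.0% | 26.4% | 26.0% | 25.0% / 24.9% |
| 9 | 39.7% | 41.2% | 40.9% | 39.7% / 39.7% |
| 12 | 50.0% | 51.3% | 51.1% | 49.9% / 50.0% |

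Closing-date censoring is about 1 to 1.5 points too high here. A separate simulation with 24-month accrual gave up to 1.6 (26.6% against 25.0%). The standard error of the estimate is 7 to 11 points. With a 24-month tail the two rules gave identical means in every setting, within 0.1 point of the truth. Visits are more frequent while patients are on treatment, so the true gap is often shorter than the 12 weeks used here.

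**The case against.** The strongest reply is that the plan already contains what is needed. The later passage of 13.4.2.3 is the specific rule and can be read as governing, which leaves the second sentence as a loose general statement. Sections 8.1 and 13.5.4 agree on 24 months. Section 8.2 gives only an anticipated timeline in a recruitment paragraph, and its 8-week minimum matches the first restaging (4 cycles of 14 days), so it may describe treatment and response follow-up. Section 13.5.4 holds the Final Analysis until survival data are in. On that reading no bias arises.

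Much of this stands, and it rules out several stronger readings that a reader might infer.

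- *Three incompatible ends of follow-up.* There is one agreed window, one timeline that cannot contain it, and a contact list that stops short within the sentence that states 24 months.
- *12-month survival resting on patients with about 6 months of follow-up.* Only the last-enrolled patients would have so little, and only if the database closed on the date in 8.2, against 13.5.4. Even then 75% to 80% of patients would have at least 12 months of potential follow-up. Administrative censoring does not bias Kaplan-Meier. It costs some precision: a standard error of 0.105 against 0.102 at a 9-month median with 27 months of recruitment.
- *A bias of 19% to 38%.* The chance that a patient alive at one contact dies within the next 12 weeks is 1 − 2^(−2.76/9) = 19% to 1 − 2^(−2.76/4) = 38% at medians of 9 and 4 months. That is not the error in the planned estimate.
- *Lost patients carried as alive to closing.* This would add about 1.5 to 6 points if 5% to 20% were lost in the first 12 months. But the loss rates are assumed, and 13.4.2.3 has an explicit rule for lost patients that avoids the error.
- *Follow-up certain to last at least 48 to 54 months.* The window is a cap that ends at death. With exponential survival at medians of 4 to 9 months, only 2^(−24/4) = 2% to 2^(−24/9) = 16% survive 24 months.

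What the reply does not remove is that both censoring sentences are in force as written, without a stated precedence.

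**Conclusion.** The inconsistency in 13.4.2.3 is real and minor. Applied without a contact at closing, the closing-date sentence overstates 12-month overall survival by about 1 to 1.6 percentage points if follow-up closes 6 months after the last entry, and by essentially nothing if the 24-month window is completed. Last-contact censoring is unbiased in both cases. These sizes rest on uniform accrual, exponential survival with medians of 4 to 12 months, and 12-week contacts.

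The mismatch between 8.2 and the survival window, and the list ending at Month 18, are matters of consistency. They do not show that the analysis will be run early. Overall survival is a secondary endpoint estimated without a test, and the two-stage decision on objective response rate is unaffected.

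**What to change.** In 13.4.2.3, delete the second sentence and censor every patient not known to have died at the date last known alive. The section's existing list of study procedures can stay as one source for that date. Make the change before overall survival is analysed, so that the rule is not chosen with the data in view.

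As consistency edits:

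- In 8.2, state that 30 to 36 months does not cover survival follow-up, or restate it as up to about 48 to 54 months plus time on treatment.
- In 8.1, align the contact list with the 24-month window, for example by adding Months 21 and 24.

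The cost is wording in three places and, if the list is extended, up to two further survival contacts for patients still alive. Sample size and the response-rate design do not change.
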